10.3. Level of Significance

This study defines a single primary endpoint with a single primary analysis. The study will be claimed to have achieved the primary efficacy objective when the primary endpoint shows a significant result at a 2-sided alpha level of 0.05 at final analysis. The secondary efficacy endpoints will be analyzed only when the study has reached the efficacy objective in the primary endpoint. The key secondary efficacy variables will be tested following a fixed-sequence-testing procedure with each at the 2-sided alpha level of 0.05 in the order below:

1. The proportion of participants who have a $\geq 50\%$ reduction from baseline to Week 24 in the MFSAF TSS.
2. OS.

Other secondary [REDACTED] endpoints will be tested using a 2-sided, 5% significance level but are not considered alpha-controlled hypotheses.

10.4. Statistical Analyses

10.4.1. Primary and Secondary Analyses

The methods and populations for primary and secondary analyses are provided in [Table 17](#).

Table 17: Primary and Secondary Analyses Methods and Populations

Endpoint	Statistical Method	Analysis Population	Primary (P) or Supportive (S)
Primary endpoint			
Proportion of participants achieving $\geq 35\%$ reduction in spleen volume from baseline to Week 24 as measured by MRI (or CT scan in applicable participants)	CMH test stratified by baseline (or screening, if applicable) platelet count ($\geq 100 \times 10^9/L$ vs 50 to $< 100 \times 10^9/L$ inclusive) and DIPSS category (intermediate-1 vs intermediate-2 vs high) at randomization	ITT	P
		PP	S
Secondary endpoints			
Proportion of participants who have a $\geq 50\%$ reduction in TSS from baseline to Week 24 as measured by the MFSAF v4.0 diary	CMH test stratified by baseline (or screening, if applicable) platelet count ($\geq 100 \times 10^9/L$ vs 50 to $< 100 \times 10^9/L$ inclusive) and DIPSS category (intermediate-1 vs intermediate-2 vs high) at randomization	ITT	P
		PP	S
Time to the first $\geq 50\%$ reduction in TSS as measured by the MFSAF v4.0 diary	Inference: Log-rank test with stratification of baseline (or screening, if applicable) platelet count ($\geq 100 \times 10^9/L$ vs 50 to $< 100 \times 10^9/L$ inclusive) and DIPSS category (intermediate-1 vs intermediate-2 vs high) at randomization Estimation: Kaplan-Meier	ITT	P

Table 17: Primary and Secondary Analyses Methods and Populations (Continued)

Endpoint	Statistical Method	Analysis Population	Primary (P) or Supportive (S)
OS determined from the date of randomization until death due to any cause	Inference: Log-rank test stratified by baseline (or screening, if applicable) platelet count ($\geq 100 \times 10^9/L$ vs 50 to $< 100 \times 10^9/L$ inclusive) and DIPSS category (intermediate-1 vs intermediate-2 vs high) at randomization Estimation: Kaplan-Meier	ITT	P
		PP	S
	Inference: Cox regression model including treatment group, baseline (or screening, if applicable) platelet count ($\geq 100 \times 10^9/L$ vs 50 to $< 100 \times 10^9/L$ inclusive), and DIPSS category (intermediate-1 vs intermediate 2 vs high) at randomization	ITT	S
OS adjusted for crossover using rank preserving structural failure time	Inference: Cox regression model including treatment group, baseline (or screening, if applicable) platelet count ($\geq 100 \times 10^9/L$ vs 50 to $< 100 \times 10^9/L$ inclusive), and DIPSS category (intermediate-1 vs intermediate 2 vs high) at randomization	ITT	S
Time to the first $\geq 35\%$ reduction in spleen volume	Inference: Log-rank test with stratification of baseline (or screening, if applicable) platelet count ($\geq 100 \times 10^9/L$ vs 50 to $< 100 \times 10^9/L$ inclusive) and DIPSS (intermediate-1 vs intermediate-2 vs high) at randomization Estimation: Kaplan-Meier	ITT	P
Duration of maintenance of a $\geq 35\%$ reduction in spleen volume	Estimation: Kaplan-Meier	ITT with spleen response	P

Other secondary endpoints, including change and percentage change in MFSAF TSS over time from baseline to Week 24 as measured by the MFSAF v4.0 diary, will be summarized descriptively by treatment group.

For the stratifications of platelet and DIPSS, within a platelet category, in the event that a particular DIPSS stratification level has fewer than 30 participants randomized, it will be combined with the nearest adjacent DIPSS level (eg, Intermediate-1 vs Intermediate-2 vs High). For example, if too small, Intermediate-1 or High risk will be merged with Intermediate-2. If Intermediate-2 has too few participants, then it will be merged with the smaller of the 2 adjacent strata.

In the event that 2 DIPSS stratification levels are combined, a sensitivity analysis for the primary endpoint without combining levels will be conducted.

The primary endpoint will also be compared between treatment groups within each of the following subgroups:

- Baseline platelet count ($\geq 100 \times 10^9/L$ vs 50 to $<100 \times 10^9/L$ inclusive) (Note that if a participant's platelet count is $< 50 \times 10^9/L$ at baseline, the platelet count at screening will be used instead)
- DIPSS category (Intermediate-1 vs Intermediate-2 vs High)
- Sex: male and female
- Age group: ≤ 65 years or > 65 years
- MF type: PMF or PPV-MF/PET-MF
- Presence/absence of V617F mutation at baseline
- Presence/absence of HMR mutations at baseline
- Baseline spleen volume group: \leq median or $>$ median
- Baseline spleen palpation size group: ≤ 10 cm or > 10 cm
- Race: white/Caucasian, black/African American, Asian, American Indian/Alaska Native, Native Hawaiian/Pacific Islander, or other
- Ethnicity: Hispanic/Latino, not Hispanic/Latino, or other

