10. STATISTICS

10.1. Sample Size Determination

The primary endpoint of this study is the proportion of participants with $\geq 35\%$ spleen volume reduction from baseline to Week 24 as measured by MRI (or CT scan in applicable participants). The primary endpoint will be analyzed by CMH test stratified by DIPSS (intermediate-1 vs intermediate-2 vs high) and baseline (or screening, if applicable) platelet count ($\geq 100 \times 10^9/L$ vs 50 to $< 100 \times 10^9/L$ inclusive; note that if a participant's platelet count is $< 50 \times 10^9/L$ at baseline, the platelet count at screening will be used for stratification/randomization). Assuming a 58.2% (29.4%) response rate for participants with normal (low) platelet count for the ruxolitinib plus piasalisib group versus 41.0% (17.2%) response rate for participants with normal (low) platelet count for the ruxolitinib plus placebo group, to achieve 83.67% power to detect a statistically significant difference with a 2-sided Type I error of 5%, a sample size of 440 participants is required to be randomized equally between treatment groups.

For the key secondary endpoint of proportion of participants who have a $\geq 50\%$ in MFSAF TSS from baseline to Week 24, assuming a response rate of 61.7% (50.0%) for participants with normal (low) platelet count for the ruxolitinib plus piasalisib group and a response rate of 45.9% (34.5%) for participants with normal (low) platelet count for the ruxolitinib plus placebo group, a sample size of 440 will provide 80.02% power using CMH test given a 2-sided Type I error of 5%.

A test for OS will be performed when 85 deaths are observed using the log-rank test stratified by platelet count and DIPSS at baseline at a 2-sided Type I error level of 0.05. The log-rank test will provide 80% power to detect a hazard ratio of 0.54. Assuming a median survival time of 5.3 years for ruxolitinib plus placebo and enrollment duration is 1.5 years, the expected time to analysis from the first participant randomized is 3 years.

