7.4.3. Overall Survival

Overall survival is defined as the interval between the randomization date and the date of death due to any cause. Date of death will be determined using the Death Report, the Survival Follow-Up, and the Participant Status eCRFs. Participants who are lost-to-follow-up or still alive at the time of analysis will be right-censored at the earlier of the date the participant was last known alive and the clinical data cutoff date for the analysis. The last known alive date is defined as the later of the last study visit and the date the participant was last known alive from the Survival Follow-Up and Participant Status eCRFs. Partial death dates will be handled using the rules described in Section 4.1.5.

[figure not shown]
The treatment difference in survival for parsaclisib plus ruxolitinib and placebo plus ruxolitinib will be assessed by a log-rank test on the ITT population and PP population stratified for baseline (or screening, if applicable) platelet and DIPSS category. The strata identified in the randomization process will be used for the analysis. In the event that stratification level combinations have limited numbers of participants, 1 or more of the strata may be combined to better facilitate estimation of the overall HR.

[figure not shown]
The hazard ratio estimate and CIs will be estimated based on a stratified Cox proportional hazards model using the same stratification factors as for the log-rank test with Efron's method (1977) accounting for ties in death days.

[figure not shown]
Kaplan-Meier time-to-event curves will be presented by treatment groups. Median survival will be estimated using the KM method. Confidence intervals for median survival time will be calculated using the generalization of Brookmeyer and Crowley's method (1982) with log-log transformation (Klein and Moeschberger 1997).

[figure not shown]
The ITT population will be used for the analysis of OS.

[figure not shown]
A sensitivity analysis of OS will be analyzed using rank preserving structural failure time method to adjust the bias in OS due to crossover.

[figure not shown]

[figure not shown]

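### The Cox inference named for crossover-adjusted OS leaves out the uncertainty of the RPSFT adjustment, so its interval is too narrow when crossover is substantial

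*Protocol*

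**What the plan says.** In Protocol Table 17 the primary OS analysis is the stratified log-rank test in the ITT population. Among the supportive rows is "OS adjusted for crossover using rank preserving structural failure time". Its method entry begins "Inference: Cox regression model including treatment group, baseline (or screening, if applicable) platelet count", and it is the same entry as for the unadjusted supportive Cox row.

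SAP 7.4.3 gives the adjusted analysis one sentence: "A sensitivity analysis of OS will be analyzed using rank preserving structural failure time method to adjust the bias in OS due to crossover". The only interval method in that section for the OS hazard ratio is this: "The hazard ratio estimate and CIs will be estimated based on a stratified Cox proportional hazards model". SAP 11.1 records no change to the protocol-defined analyses, and SAP Appendix A plans a dedicated output (Table 2.2.2.7.3). Neither document mentions a bootstrap, a confidence set from g-estimation, retention of the ITT p-value, or recensoring.

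On crossover, Protocol 4.1.2 opens it once the last participant's Week 24 data are clean and frozen, subject to the hematology criteria of Protocol 6.4. Protocol 4.1.3 allows it earlier for defined spleen growth. The expected share of the placebo arm that crosses over is not stated.

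**The concern.** RPSFT estimates an acceleration parameter, psi, from the trial's own data. It then uses psi to rebuild the survival times that placebo participants who switched would have had without parsaclisib. A Cox model fitted to those times takes them as data, so its standard error is conditional on psi and leaves out the sampling error in psi. RPSFT uses no information beyond the randomized comparison, so its evidence against no effect should be that of the ITT test. A smaller Cox p-value is an artifact.

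At stake is how the adjusted hazard ratio is read. Shown beside the ITT result, it would carry error bars that are too tight, and its interval could exclude 1 when the ITT test is not significant.

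**Working it through.** **Inputs.** From Protocol 10.1: 440 participants, 1:1; OS tested at 85 deaths with 2-sided alpha 0.05; stated power, "The log-rank test will provide 80% power to detect a hazard ratio of 0.54"; control median OS 5.3 years, with accrual over 1.5 years; OS analysis expected 3 years after first randomization. Derived: general crossover opens no earlier than 1.5 + 24/52 = 1.96 years, taken as 2.0. Assumed, because the documents give no figure: 10% to 80% of placebo participants willing to cross over.

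**Step 1: the plan's own power.**
- Schoenfeld: Φ(√85/2 × |ln 0.54| − 1.96) = Φ(4.610 × 0.616 − 1.96) = 81.1%.
- Freedman: Φ(√85 × 0.46/1.54 − 1.96) = 78.6%.
- The two bracket the stated 80%. The matching event counts, 83 and 88, bracket 85.
- With exponential survival and uniform accrual, the 85th death falls at 2.91 years under HR 0.54, in line with the stated 3 years, and at 2.40 years under no effect. Crossover therefore opens before the OS analysis.

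**Step 2: Cox on RPSFT times.** The trial was simulated with crossover at 2.0 years and cutoff at the 85th death. Psi was found by log-rank g-estimation, and an unstratified Cox model compared observed parsaclisib times with reconstructed placebo times. There were 6,000 trials per row. With 80% willing, 68% of the placebo arm switched; with 50%, 42–43%.

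| True HR, share willing | Recensoring | Mean Cox SE | Empirical SD | Ratio | 95% CI coverage | Adjusted Cox rejects | ITT log-rank rejects |
|---|---|---|---|---|---|---|---|
| 0.54, 80% | yes | 0.277 | 0.327 | 0.85 | 89.9% | 61.8% | 49.9% |
| 0.54, 80% | no | 0.225 | 0.297 | 0.76 | 85.9% | 73.1% | 49.9% |
| 0.54, 50% | yes | 0.283 | 0.314 | 0.90 | 92.8% | 59.5% | 63.4% |
| 0.54, 50% | no | 0.225 | 0.259 | 0.87 | 91.3% | 76.1% | 63.4% |
| 1.0, 80% | yes | 0.226 | 0.260 | 0.87 | 92.4% | 7.5% | 5.1% |
| 1.0, 80% | no | 0.219 | 0.266 | 0.82 | 89.7% | 10.2% | 5.1% |
| 1.0, 50% | yes | 0.226 | 0.247 | 0.91 | 93.9% | 6.1% | 4.7% |
| 1.0, 50% | no | 0.219 | 0.245 | 0.89 | 92.4% | 7.6% | 4.7% |

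At 10% willing (1,000 trials) coverage was 93.7% to 95.4%.

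The shortfall comes from the standard error, not from bias. At HR 0.54 and 80%, the median adjusted HR was 0.546 with recensoring and 0.539 without. The SE ratio alone predicts coverage of 2Φ(1.96 × 0.85) − 1 ≈ 90% and 2Φ(1.96 × 0.76) − 1 ≈ 86%.

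**Step 3: other crossover times and shares.**
- Crossover at 2.1 years, recensored, 4,000 trials: coverage at HR 0.54 was 91.8% (80%), 93.9% (50%) and 95.1% (25%). Null rejection was 6.8%, 5.9% and 5.2%, against 4.7% for ITT.
- Crossover at 2.25 years: null rejection was 6.0% (80%) and 5.4% (50%).
- A further 700 trials at 2.1 years, 80%, HR 0.54: SD 0.333 against Cox SE 0.282 with recensoring; coverage 91% with recensoring and 87% without.

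**Step 4: does a bootstrap repair it?** 200 trials with 150 resamples each, 80% willing, psi re-estimated in every resample; Monte Carlo error about 2 points.

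| True HR | Recensoring | Cox interval | Percentile bootstrap | Normal interval, bootstrap SE | Percentile/Cox width |
|---|---|---|---|---|---|
| 0.54 | yes | 90.0% | 95.0% | 98.0% | 1.27 |
| 0.54 | no | 84.0% | 93.0% | 93.0% | 1.28 |
| 1.0 | yes | 91.0% | 91.0% | 96.5% | 1.17 |
| 1.0 | no | 89.5% | 92.0% | 92.0% | 1.19 |

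Only the bootstrap-SE interval with recensoring kept at least 95% in both cases, and it is somewhat conservative at HR 0.54. An interval scaled to reproduce the ITT p-value covered 92.0% (80%) and 89.3% (50%) at HR 0.54, so it is not a substitute.

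**The case against.** The best defence is that the plan is silent rather than wrong. Neither document says that the standard error is model-based, and a bootstrap around the Cox hazard ratio would be consistent with Table 17. The first part stands. But the table puts the Cox model under inference, repeats the entry of the unadjusted row, and is backed by a SAP whose only OS interval method is Cox. Someone following the plan as written would produce the interval tested above.

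Three stronger readings are tempting and do not hold:
- A reader might infer that every placebo participant is offered crossover. Protocol 4.1.2 and 6.4 make it conditional on platelet and neutrophil counts, and participants who have died or stopped treatment by then are not candidates. The 80% scenario is the top of an assumed range. Time spent on image reading, data cleaning and the freeze moves crossover later and shrinks the error.
- A reader might infer that the adjusted analysis will always look more significant than ITT. At HR 0.54 and 80% it does. At 50% with recensoring it rejected less often (59.5% against 63.4%).
- A reader might infer much larger errors by letting follow-up run well past 85 deaths. Neither document plans such an OS analysis.

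The Step 2 simulation also has no strata and no dropout, whereas Table 17's model includes platelet count and DIPSS.

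**Conclusion.** The point holds as a defect in one supportive analysis. At the planned 85 deaths and HR 0.54, nominal 95% intervals cover about 90–92% with recensoring and 86–87% without at 80% crossover, about 93–94% and 91–92% at 50%, and close to 95% at 25% or less. Under no effect at 80% crossover, the adjusted Cox test rejects in about 6–7.5% of trials with recensoring and about 10% without, against about 5% for the ITT log-rank test.

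These figures rest on exponential survival, a common treatment effect, crossover at 2.0 to 2.25 years and an assumed crossover share. A reader might infer that the trial's OS claim is at risk. It is not: the alpha-controlled OS test is the unadjusted ITT stratified log-rank test (Protocol 10.3 and Table 17; SAP 3.2), which this does not touch. The plan should still be corrected, because the rule as written gives wrong error bars and the repair is cheap.

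**What to change.** In Protocol Table 17 and SAP 7.4.3:
- State that the RPSFT-adjusted hazard ratio is an estimate and that recensoring is applied.
- Take its 95% CI from a bootstrap that repeats g-estimation, recensoring and the Cox fit in each resample. Name the interval type: a normal approximation on the log hazard ratio with the bootstrap SE, since percentile intervals covered only 91–92% at HR 1.0.
- Report the ITT stratified log-rank p-value, and no Cox p-value from the adjusted data.

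Settle this before unblinding, so that the choice of interval cannot be questioned afterwards. The cost is a sentence or two in each document, computing time and a wider interval (the percentile bootstrap interval was about 1.2 to 1.3 times the Cox width at 80% crossover). Study conduct and sample size do not change.

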7.3.2. Subgroup Analyses for Primary Endpoint

Subgroups will be formed based on the following participant characteristics and baseline variables for those participants whose data are available:

- Sex: male and female
- Age group: ≤ 65 years or > 65 years
- MF type: PMF or PPV-MF/PET-MF
- Presence/absence of V617F mutation at baseline
- Presence/absence of HMR mutations at baseline
- Baseline spleen volume group: \leq median or $>$ median
- Baseline spleen palpation size group: ≤ 10 cm or > 10 cm
- Race: White/Caucasian, Black/African-American, Asian, American-Indian/Alaska Native, Native Hawaiian/Pacific Islander, or other
- Ethnicity: Hispanic/Latino, not Hispanic/Latino, or other
- Platelet: $\geq 100 \times 10^9/L$ vs 50 to $< 100 \times 10^9/L$, inclusive using baseline platelet counts. Note that if a participant's platelet count is $< 50 \times 10^9/L$ at baseline, the platelet count at screening will be used for stratification/randomization.
- DIPSS: intermediate-1, intermediate-2, or high

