2.1 Primary Efficacy			
2.1.1.1	Cochran-Mantel-Haenszel Test of Proportion of Participants With $\geq 35\%$ Reduction in Spleen Volume at Week 12 and Week 24	ITT	
2.1.1.2	Cochran-Mantel-Haenszel Test of Proportion of Participants With $\geq 35\%$ Reduction in Spleen Volume at Week 12 and Week 24	PP	
2.1.2.1	Cochran-Mantel-Haenszel Test of Proportion of Participants With $\geq 35\%$ Reduction in Spleen Volume at Week 12 and Week 24 – by Sex	ITT	
2.1.2.2	Cochran-Mantel-Haenszel Test of Proportion of Participants With $\geq 35\%$ Reduction in Spleen Volume at Week 12 and Week 24 – by Age Group	ITT	
2.1.2.3	Cochran-Mantel-Haenszel Test of Proportion of Participants With $\geq 35\%$ Reduction in Spleen Volume at Week 12 and Week 24 – by MF Type	ITT	
2.1.2.4	Cochran-Mantel-Haenszel Test of Proportion of Participants With $\geq 35\%$ Reduction in Spleen Volume at Week 12 and Week 24 – by Presence/Absence of V617F Mutation at Baseline	ITT	

Table No.	Title	Population	Standard
2.1.2.5	Cochran-Mantel-Haenszel Test of Proportion of Participants With $\geq 35\%$ Reduction in Spleen Volume at Week 12 and Week 24 – by Presence/Absence of HMR Mutations at Baseline	ITT	
2.1.2.6	Cochran-Mantel-Haenszel Test of Proportion of Participants With $\geq 35\%$ Reduction in Spleen Volume at Week 12 and Week 24 – by Baseline Spleen Volume Group	ITT	
2.1.2.7	Cochran-Mantel-Haenszel Test of Proportion of Participants With $\geq 35\%$ Reduction in Spleen Volume at Week 12 and Week 24 – by Baseline Spleen Palpation Size Group	ITT	
2.1.2.8	Cochran-Mantel-Haenszel Test of Proportion of Participants With $\geq 35\%$ Reduction in Spleen Volume at Week 12 and Week 24 – by Race	ITT	
2.1.2.9	Cochran-Mantel-Haenszel Test of Proportion of Participants With $\geq 35\%$ Reduction in Spleen Volume at Week 12 and Week 24 – by Ethnicity	ITT	
2.1.2.10	Cochran-Mantel-Haenszel Test of Proportion of Participants With $\geq 35\%$ Reduction in Spleen Volume at Week 12 and Week 24 – by Platelet Count	ITT	
2.1.2.11	Cochran-Mantel-Haenszel Test of Proportion of Participants With $\geq 35\%$ Reduction in Spleen Volume at Week 12 and Week 24 – by DIPSS	ITT	

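### Subgroup analysis of the primary endpoint tests treatment separately within 28 levels and plans no interaction test, so it cannot show whether the effect differs between levels (a cheap improvement)

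*Protocol*

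**What the plan says.** - Protocol 10.4.1: "The primary endpoint will also be compared between treatment groups within each of the following subgroups". The factors are platelets (2 levels), DIPSS (3), sex (2), age (2), MF type (2), V617F (2), HMR (2), baseline spleen volume (2), palpated spleen size (2), race (6) and ethnicity (3).
- SAP 7.3.2 lists the same 11 factors: "Subgroups will be formed based on the following participant characteristics and baseline variables for those participants whose data are available". It names no test.
- The only visible method is in the table titles of SAP Appendix A, under Primary Efficacy. Each of Tables 2.1.2.1 to 2.1.2.11 is titled as a CMH test of the 35% response, for example "Reduction in Spleen Volume at Week 12 and Week 24 – by Sex".
- Protocol 10.3: "This study defines a single primary endpoint with a single primary analysis". The fixed sequence after it holds the TSS response and then OS. Other secondary (and redacted) "endpoints will be tested using a 2-sided, 5% significance level but are not considered alpha-controlled hypotheses". That sentence concerns endpoints, not subgroup tests of the primary endpoint.
- The rules for merging small DIPSS strata (fewer than 30 in Protocol 10.4.1; fewer than 10 as an example in SAP 7.1) concern stratification of the CMH test. No rule covers small subgroup levels.

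The visible text on subgroups has no interaction test, no multiplicity rule, no minimum level size and no exploratory label.

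**The concern.** A subgroup analysis asks whether the treatment effect differs between, say, men and women. A p-value for men and another for women do not answer that. The smaller level can miss significance through size alone while the effect is the same in both. An interaction test addresses the question directly, and none is planned.

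The result could mislead in two ways. If parsaclisib works as planned, the tables will probably show several factors that are significant in one level and not in the other, and a reader may conclude that some patients do not benefit. If it does not work, 28 tests give many chances for an isolated nominal p<0.05. Either pattern bears on what is said about who should receive the combination.

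**Working it through.** **Inputs.** From Protocol 10.1: 440 participants, 1:1, two-sided 5%; response 58.2% vs 41.0% with normal platelets and 29.4% vs 17.2% with low platelets; stated power 83.67%. From Protocol 10.5: Z > 0.18 at 100 participants, > 1.28 at 220 and > 1.96 at 440. Not given, so assumed: the low-platelet share (20-30%) and the sizes of the other subgroup levels.

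**1. The plan's own power figure.** With n per arm in each platelet stratum, the expected CMH statistic is Z = Σ(n/2)(p1−p0) / √Σ[(n/2)² · 2p̄(1−p̄)/n]. At a 25% low-platelet share, n is 55 and 165:
- numerator: 27.5 × 0.122 + 82.5 × 0.172 = 17.55
- variance: 4.91 + 20.62 = 25.54, square root 5.05
- Z = 3.47, so fixed-sample power is Φ(3.47 − 1.96) = 93%.

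This exceeds 83.67%. Requiring all three hurdles gives 84.0% at a 20% share and 83.5% at 25%, which agrees with the stated figure. The same rule gives 80.2% for the TSS response (stated 80.02%).

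**2. The planned effect is uniform on the odds-ratio scale.** Normal platelets: (0.582/0.418)/(0.410/0.590) = 2.00. Low platelets: (0.294/0.706)/(0.172/0.828) = 2.00.

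**3. What within-level tests do with a uniform effect.** In a level holding a fraction f of the trial, expected Z is about 3.47√f.
- 50/50 factor: Z = 2.45 and power 0.69 in each level. Chance of discordance: 2 × 0.69 × 0.31 = 0.43.
- 60/40 factor: Z = 2.69 and 2.20, power 0.77 and 0.59. Discordance: 0.77 × 0.41 + 0.23 × 0.59 = 0.45.
- Platelets 75/25: power 0.88 and 0.33. Discordance: 0.88 × 0.67 + 0.12 × 0.33 = 0.63.

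Platelets plus seven factors at about 0.44 gives 0.63 + 7 × 0.44 = 3.7 discordant factors of 8. The factors share the same participants, so the chance of at least one needs simulation. With 440 participants, a platelet-stratified CMH test per level and factors assumed independent of one another, at least one binary factor was discordant in 89-93% of trials over low-platelet shares of 20-30%. The mean was 3.6 to 3.8. Over all 28 levels, about 14 reach p<0.05 and about 14 do not, although every level truly benefits.

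**4. No effect anywhere.** Independent tests would give 1 − 0.95^28 = 76% for 28 tests, and 1 − 0.95^56 = 94% if Week 12 doubles them. Simulation allows for the overlap. The ranges below run from skewed to more even level sizes:

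| | Week 24 (28 tests) | Weeks 12 and 24 (56 tests) |
|---|---|---|
| p<0.05 in either direction | 49-59% | 71-81% |
| p<0.05 favouring parsaclisib | 27-32% | 41-49% |

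Given a non-significant primary result, the chance of a Week 24 subgroup favouring parsaclisib is about 29%. These figures assume that the trial runs to the end. If the spleen hurdles at both interims were followed, about 9% of no-effect trials would pass them (treating the interim statistics as earlier looks at the same test).

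**5. After the change.** Eleven interaction tests at 5% each give at least one false positive in 1 − 0.95^11 = 43% of trials if independent, and in about 40% by simulation. An interaction test therefore answers the right question but does not remove chance findings.

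**The case against.** A reader might infer that false subgroup claims are more likely than not. The documents do not support that:
- A nominal p-value in a table is not a claim. Protocol 10.3 and SAP 3.2 confine confirmatory claims to one primary analysis and a fixed sequence, and no text lets a subgroup support one.
- The above-one-half figures need no effect anywhere, a 5% threshold that the documents do not set for subgroups, and counting of results in either direction. For an apparent benefit of parsaclisib, every figure is below one half.
- The interim rules, although nonbinding, would stop most no-effect trials if followed.

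A reader might also infer that the primary endpoint itself is tested at two time points. It is defined at Week 24 only. Week 12 enters through the Appendix A titles, and that appendix calls its lists guidelines.

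It is also fair to say that discordance between levels only reflects lower power in smaller groups, and that neither document proposes reading non-significance as absence of effect. The table shells are in a separate document and may show estimates and intervals. Parts of both documents are redacted, so a label elsewhere cannot be excluded.

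All of this limits the point to reporting and interpretation. It does not answer the core: the only stated subgroup method does not address whether the effect differs, and the two subgroup sections, where an interaction test or a label would belong, contain neither.

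**Conclusion.** The point holds as a cheap improvement. The stated method cannot separate real heterogeneity from differences in level size, and the tables would probably look heterogeneous even if the planned uniform effect were true. That risk needs no failed trial, only the plan's own assumptions. The chance-finding risk under no effect is real but smaller, and it is conditional on the trial continuing. The primary test and its type I error are untouched.

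The discordance and chance-finding figures rest on the assumed level sizes, the assumed low-platelet share and, in the simulations, independence between factors. The Week 12 figures also rest on an assumed correlation with Week 24. The count of 28 levels and the absence of an interaction test in the visible text do not depend on these assumptions.

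**What to change.** In Protocol 10.4.1, SAP 7.3.2 and Tables 2.1.2.1 to 2.1.2.11:
1. For Week 24, report the response difference or odds ratio with its 95% CI for each level in a forest plot. The odds ratio matches the hypothesis in SAP 7.2 and is the scale on which the planned effect is uniform; the planned differences are 17.2 and 12.2 points.
2. Replace within-level p-values with one treatment-by-factor interaction test per factor, from a logistic model with treatment, factor, their interaction and the randomisation strata.
3. State a minimum level size. Below it, pool the level or only describe it; the small race groups are the obvious case.
4. State that all subgroup results, including the interaction tests, are exploratory and support no efficacy claim, whatever the primary result.

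The cost is wording and table shells, with no new data or participants, and the change should be made before unblinding. There are three downsides. Interaction tests have low power. Eleven unadjusted ones carry about a 40% chance of at least one false positive, which is why the label must cover them. The nominal within-level p-values are given up.
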